5.3.3 Basal insulin

Subjects may enter the trial on a stable dose of basal insulin. A stable dose of basal insulin (intermediate acting human insulin, intermediate acting insulin analogue or long acting insulin analogue) is defined as basal insulin adjustments up to 15% at the investigator's discretion. Subjects treated with basal insulin must initiate treatment with metformin as described in section 5.3.).

The pre-trial basal insulin regimen will be considered background medication and will not be provided by Novo Nordisk.

Subjects treated with basal insulin at screening should reduce their basal insulin dose by 20% at randomisation.

Subjects on a stable dose of metformin ≥ 2000 mg as per section 5.3.1 can advance directly to maintenance period or randomisation depending on the time on stable insulin:

- Subjects with a stable dose of basal insulin for at least 30 days but less than 56 days at screening (visit 1) may proceed directly to the 8 week maintenance period (Visit 5)
- Subjects on a stable dose of basal insulin for 56 days or more at screening (Visit 1) may advance directly to randomisation (Visit 7) when eligibility according to the inclusion and exclusion criteria has been confirmed.

After the MTD dose of liraglutide/liraglutide placebo is reached, the dose of basal insulin can be up-titrated to no higher than the screening dose level. This up-titration will be based on the average of three pre-visit fasting SMPG values before visits between weeks 4 and 8 (Visits 10A -11B). Up-titration is only allowed between Visits 10A and 11B. Up-titration of basal insulin dose is to be performed at the discretion of the investigator in accordance with the algorithm described in Table 5-1.

Table 5–1 Algorithm for up-titration of basal insulin dose

Average fasting SMPG	Increase in basal insulin dose
>10 mmol/L (>180 mg/dL)	+6 units
7.8 to 10 mmol/L (141–180 mg/dL)	+4 units
6.7 to <7.8 mmol/L (121–140 mg/dL)	+2 units
5.6 to <6.7 mmol/L (100–120 mg/dL)	+1 units

SMPG=self-measured plasma glucose

(adapted from the Texas Diabetes Council 2013²¹)

Basal insulin should be down-titrated for unexplained hypoglycaemia ≤ 3.9 mmol/L (≤ 70 mg/dL) at any time during the trial at the discretion of the investigator in accordance with Table 5-2

Table 5–2 Algorithm for down-titration of basal insulin dose

PG	Reduction of basal insulin dose

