17.1 Sample size calculation

The sample size has been determined in order to demonstrate superiority of liraglutide in combination with metformin with or without basal insulin treatment vs. liraglutide placebo with metformin with or without basal insulin treatment, with regards to change in HbA_{1C} from baseline after 26 weeks, using a significance level of 5% and a two-sided test.

The sample size is based on calculations for the primary endpoint alone. Assumptions for the sample size calculations are as follows:

Change in HbA_{1c}: a mean difference of 0.9% of liraglutide in combination with metformin with or without basal insulin treatment vs. liraglutide placebo with metformin with or without basal insulin treatment; Standard deviation (SD) =1.2%. The change in mean difference was chosen based on the effect of liraglutide vs. placebo observed in the adult population (LEAD 1, 2, 4 and 5 trials)¹⁵ and a paediatric PK/PD trial which included HbA_{1c} after 5 weeks of treatment as an exploratory endpoint (NN2211-1800)³⁶.

The chosen withdrawal rates (see table 17.1) are based on the withdrawal rates seen in the LEAD 2 trial¹⁵ where the withdrawal rate was approximately 40% for the placebo group and approximately 20% for the active groups. A slightly higher withdrawal rate is assumed as the trial is performed in a paediatric population. Therefore, the withdrawal rate for the active group is assumed to be 22%. The primary analysis will impute measurements for withdrawn placebo subjects based on placebo completers, and thus the sample size is not adjusted for placebo withdrawal rate.

Based on these assumptions, the sample size is set to 47 in each of the liraglutide and liraglutide placebo arms for the full analysis set (FAS) in order to achieve 80% power see [Table 17-1](#).

Assuming a screening failure rate of 65%, 269 subjects will need to be screened.

Table 17-1 Total sample size for a 1:1 randomisation

		Difference to detect in subjects with week 26 data				
Withdrawal rate		0.6%	0.7%	0.8%	0.9%	1.0%
20	Adjusted difference	0.48%	0.56%	0.64%	0.72%	0.80%
	Sample size	200	148	114	90	74
22	Adjusted difference	0.47%	0.55%	0.62%	0.70%	0.78%
	Sample size	210	154	120	94	78
25	Adjusted difference	0.45%	0.53%	0.60%	0.68%	0.75%
	Sample size	226	166	128	102	84

Power: 80%

Standard deviation of change in HbA_{1c} (%) from baseline at week 26 assumed to be 1.2%

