3.3 General considerations

EurdraCT No.: 2011-002605-29

Novo Nordisk will be responsible for the statistical analysis and reporting. Analysis and reporting will be based on pooled data from all sites.

The statistical analyses will be performed with a significance level of 5% (two-sided tests).

For all endpoints analysed statistically, estimated mean treatment differences will be presented together with two-sided 95% confidence intervals and p-values.

The fixed effects in the models described in the following sections are defined as:

- 'age group' is '10-14' and '>14 years' at end of trial, where age at end of trial is calculated as age at baseline + 1 year.
- 'concomitant diabetes treatment at baseline' is determined by the prescribed insulin dose at baseline. The fixed effect will be 'Y' for all subjects with a prescribed insulin dose above zero at baseline, and 'N' otherwise.
- 'region' is defined as 'Asia', 'Europe', 'North America', 'South America' and 'Rest of the world'. A list of the countries in each region can be found in the NN2211 project statistical programming specification (4).

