3.5 Primary endpoint

The primary endpoint is change from baseline to week 26 in HbA_{1c}. The FAS will be used for this analysis. All available data will be used, including data collected after treatment discontinuation and rescue initiation. A pattern mixture model using multiple imputation will be used.

The null hypothesis is no difference between the changes from baseline in HbA_{1c} (%) after 26 weeks of randomised treatment with liraglutide + metformin with or without basal insulin and liraglutide placebo + metformin with or without basal insulin (H0: d= liraglutide – placebo =0). The alternative hypothesis is that there is a difference between the two treatment arms (HA: d \neq 0). Superiority of liraglutide over liraglutide placebo will be concluded if the 95% confidence interval for the treatment difference for change from baseline in HbA_{1c} (%) after 26 weeks of randomised treatment lies entirely below 0%; implying that the two sided p-value is less than 5%.

The multiple imputation procedure will be as follows:

For subjects in the liraglutide arm who are missing their week 26 HbA_{1c} measurement, measurements will be imputed using the subjects' baseline HbA_{1c} under a regression model based on the completers from the liraglutide placebo arm. Likewise, the same imputation model will be used for subjects in the liraglutide placebo arm with missing week 26 data. Multiple imputation of

Liraglutide		Date:	25 June 2018	Novo Nordisk
Trial ID: NN2211-3659	CONFIDENTIAL	Version:	2.0	
Statistical Analysis Plan	CONFIDENTIAL	Status:	Final	
EurdraCT No.: 2011-002605-29		Page:	14 of 25	

missing week 26 HbA $_{1c}$ data will be performed by utilizing the relationship between HbA $_{1c}$ measured at baseline and weeks 10 and 14 with that measured at week 26 in placebo patients. The following four regression models will be built from the liraglutide placebo completers group for this purpose:

- Model 1: Only baseline covariates (baseline HbA_{1c}, stratification group (gender*age group), concomitant diabetes treatment at baseline)
- Model 2: Baseline covariates and week 10 HbA_{1c} as covariates
- Model 3: Baseline covariates and week 14 HbA_{1c} as covariates
- Model 4: Baseline covariates, week 10 HbA_{1c}, and week 14 HbA_{1c} as covariates

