Missing week 26 data will be imputed by selecting a random observation from a normal distribution centered at the value predicted by the regression model and with variance analogous to predicting a new observation in regression analysis. For subjects on the placebo arm, the model used will be dependent on the subjects' available HbA_{1c} data throughout the trial. For example, if a subject had HbA_{1c} measurements only at baseline and week 14, then model 3 would be used. For subjects on the liraglutide arm, the measurements will be imputed using only the subjects' baseline HbA_{1c} (model 1).

The imputation procedure will be iterated 10,000 times, thus generating 10,000 complete data sets including observed and imputed values.

For each of the imputed data sets the change in HbA_{1c} from baseline to week 26 will be analysed using an ANCOVA with treatment and stratification groups (gender*age group) as categorical fixed effects and baseline HbA_{1c} as covariate. The results obtained from analysing the datasets will be combined using Rubin's rule (1) to draw inference.

The estimated treatment difference between liraglutide and liraglutide placebo together with two-sided 95% CI and p-value for the test of no difference in effect will be presented.

Sensitivity analyses will be performed for the primary endpoint. They will include:

- 1. an analysis of covariance (ANCOVA) model with LOCF imputation for missing data. Data collected after treatment discontinuation or initiation of rescue medication will be handled as missing data. Effects in the model are treatment, stratification groups (gender*age group), and baseline HbA_{1c} as a covariate. The LOCF will be performed using data collected at time points in the treatment period (on treatment) and before initiation of rescue medication, or data at baseline if there is no data on treatment without rescue medication post baseline.
- 2. an ANCOVA model including data after treatment discontinuation or initiation of rescue treatment and LOCF imputation for missing data. Effects in the model are treatment, stratification groups (gender*age group), and baseline HbA_{1c} as a covariate. The LOCF will be performed using baseline data, if this is the only available data, and otherwise data collected at time points during the trial.

Liraglutide
Trial ID: NN2211-3659
Statistical Analysis Plan
EurdraCT No.: 2011-002605-29

Date: 25 June 2018 Version: 2.0
Status: Final
Page: 15 of 25

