- 3. multiple imputation of missing values in both treatment groups (data collected after treatment discontinuation or initiation of rescue treatment considered as missing) based on parameters estimated from the placebo group. The same model as for the primary analysis will be used.
- 4. a repeated measurement analysis (MMRM) model using all data points for all visits, but excluding data collected after treatment discontinuation or initiation of rescue medication. Fixed factors in the model are treatment, stratification groups (gender*age group), and baseline HbA_{1c} included as a covariate, all nested within visit. If possible an unstructured covariance matrix will be used.
- 5. an MMRM model as described above, but including age of the subjects at baseline as covariate, as well as concomitant diabetes treatment at baseline and region. All will be nested within visit.
- 6. multiple imputation of missing values in both treatment groups based on parameters estimated from the placebo group (the same model as for the primary analysis) based on all randomised subjects

The HbA_{1c} over time (at randomisation, week 10, 14, 26 and 52) will be presented in figures as:

- mean (SE) from the primary analysis multiple imputation, combined using Rubin's rule, at week 26 and 52
- Least square mean (SE) estimated from the MMRM model (no. 4 above) at week 10, 14, 26 and 52. The mean values of the covariate effects will be used for computation of the least square means.

The change in HbA_{1c} over time will in addition be summarised by age group and concomitant diabetes treatment at baseline (see section 3.3 for the definitions of age group and concomitant diabetes treatment at baseline). The summary of change in HbA_{1c} over time will also be shown in plots as mean (SE) both grouped by treatment alone, age group by treatment and subjects having a run-in period by treatment

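### The primary ANCOVA does not adjust for baseline basal insulin use, and no planned analysis makes that adjustment on the treatment-policy estimand: a modest point of efficiency and chance imbalance, not of validity

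*SAP*

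**What the plan says.** The primary analysis fits each imputed data set "using an ANCOVA with treatment and stratification groups (gender*age group) as categorical fixed effects and baseline" HbA1c as covariate, and combines the results by Rubin's rule (SAP 3.5; the model in Protocol 17.3 is the same). It uses all available data, including data after discontinuation and rescue, and SAP 4.1 names the target as the treatment-policy estimand.

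Baseline insulin use appears in several other places:

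- **Definition.** SAP 3.3 codes concomitant diabetes treatment at baseline as Y when the prescribed insulin dose is above zero and N otherwise. SAP 4.3 explains that this replaces the protocol's definition because all subjects were to take metformin.
- **Imputation.** Model 1 contains baseline HbA1c, "stratification group (gender*age group), concomitant diabetes treatment at baseline". Models 2 to 4 add post-baseline HbA1c to those covariates.
- **Sensitivity analysis 5.** This is an MMRM "including age of the subjects at baseline as covariate, as well as concomitant diabetes treatment at baseline and region".
- **Exploratory analysis (SAP 3.7).** This is an MMRM with a treatment-by-insulin interaction.
- **Descriptive summaries.** HbA1c change is tabulated by insulin use (SAP 3.5).

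Randomisation is stratified by sex and age group only (Protocol 5.1 and 11). Insulin-treated subjects are handled differently after randomisation: "Subjects treated with basal insulin at screening should reduce their basal insulin dose by 20% at randomisation" (Protocol 5.3.3), with up-titration allowed later, to no more than the screening dose.

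**The concern.** A baseline factor that may predict the outcome, is not balanced by design, and is already collected and coded is an obvious candidate for the primary model. If insulin use predicts week-26 HbA1c beyond baseline HbA1c and the strata, leaving it out has two consequences. The interval is wider than it needs to be, and in a trial of 94 subjects a chance imbalance in insulin use moves the observed difference.

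The analyses that do adjust do not fill the gap. Sensitivity analysis 5 and the exploratory model exclude data after discontinuation or rescue, whereas the primary analysis includes them. If the arms turned out unequal in insulin use, no pre-specified analysis would show how far this affected the primary treatment-policy result.

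**Working it through.** **Inputs from the documents.** Two-sided 5% level (SAP 3.3). From Protocol 17.1: "a mean difference of 0.9% of liraglutide in combination with metformin with or without basal insulin treatment" over placebo, "Standard deviation (SD) =1.2"%, 22% withdrawal in the active arm with no effect in those withdrawn, and 47 per arm "in order to achieve 80% power".

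**Assumptions.** The documents give no planned share on insulin and no insulin effect. Prevalence p is taken as 25-31%, with 10-50% as the outer range. The upper central value is close to the 31.1% that Protocol 5.4 cites from an incidence study in adolescents, which is not this trial's population. The residual effect b of insulin use on week-26 change, given baseline HbA1c and strata, is varied from 0 to 1.0 HbA1c points.

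**1. The plan's own figure.** The diluted difference is 0.9 x 0.78 = 0.702. The standard error is 1.2 x sqrt(2/47) = 0.2475. A two-sample t-test (noncentral t) gives 47 per arm, 94 in total, with power 80.1%. The plan's figure is reproduced.

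**2. Effect of adding the term.** Insulin explains R2 = b^2 p(1-p)/1.44 of the variance. One extra covariate costs a variance factor of about 1 + 1/85 (94 subjects less seven parameters leave 87 degrees of freedom). The SE is multiplied by sqrt[(1 - R2)(1 + 1/85)].

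Example with p = 0.31 and b = 0.5: R2 = 0.25 x 0.2139/1.44 = 0.0371, and the factor is sqrt(0.9629 x 1.0118) = 0.987, so the SE falls by 1.3%.

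| b (HbA1c points) | SE change, p = 25% | SE change, p = 31% | Power, p = 31% |
|---|---|---|---|
| 0 | +0.6% | +0.6% | 79.7% |
| 0.25 | +0.2% | +0.1% | 80.0% |
| 0.5 | -1.1% | -1.3% | 81.1% |
| 0.75 | -3.2% | -3.7% | 83.0% |
| 0.8 | -3.7% | -4.3% | 83.5% |
| 1.0 | -6.2% | -7.2% | 85.6% |

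**3. Break-even.** The factor equals 1 when R2 = 1/86, so b = sqrt[1.44/(86 p(1-p))]. This gives 0.30 at 25% and 0.28 at 31%. Over the outer range it is 0.43 at 10% and 0.26 at 50%.

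**4. Chance imbalance.** The SD of the between-arm difference in insulin use is sqrt[2p(1-p)/47]: 8.9 percentage points at 25% and 9.5 at 31%. At 31%, a difference of 10 points or more has a probability of about 29%. A 2-SD difference at 25% is about 18 points. With b = 0.5 it shifts the estimate by 0.18 x 0.5 = 0.09, which is 13% of 0.702 and 0.36 of the SE of 0.2475.

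**5. Simulation check.** Complete data, 47 per arm, four strata, a baseline covariate, p = 31%, 6,000 runs per setting. Power without and with the term was 78.6% and 78.2% at b = 0, 77.9% and 79.2% at b = 0.5, and 78.3% and 84.0% at b = 1.0. With no treatment effect and b = 0.5, the rejection rate was 4.7% without the term and 5.0% with it.

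All of these results assume complete data and ignore between-imputation variance.

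**The case against.** The strongest reply is that this is an optional choice. The ANCOVA contains treatment, every stratification factor and baseline HbA1c. Its estimate is unbiased over randomisations, and ordinary chance imbalance in an unstratified covariate is already reflected in the standard error. That stands. A reader might infer that the omission biases the primary test or inflates type I error; neither the design nor the simulation supports that.

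A reader might also see an error in an imputation model that is richer than the analysis model. This arrangement is permitted and is not a fault in itself.

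The 20% dose reduction might be taken as proof that insulin predicts the outcome. It makes a different HbA1c course plausible but does not establish one. Protocol 5.3.3 allows up-titration to the screening dose between weeks 4 and 8, Protocol section 18 says this is to keep placebo-arm treatment comparable with that before randomisation, and week 8 is 18 weeks before the endpoint.

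The model is also fixed in Protocol 17.3, and SAP 1.2 says the primary analysis was revised at a regulator's request. A change in the SAP alone would leave the two documents in conflict. This is a fair reason for care, met by an explicit entry in SAP section 4. It is not a reason to leave the primary estimand without any insulin-adjusted analysis.

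Finally, sensitivity analysis 5 does adjust for insulin. It is a partial safeguard only, because it excludes the data that define the primary estimand.

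**Conclusion.** The point holds as a minor improvement. Baseline insulin use is missing from the primary ANCOVA, was not a randomisation stratum, and is not adjusted for in any planned analysis of the treatment-policy estimand.

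One might conclude that the plan gives up precision for nothing. The documents do not support that. The term has a small cost, about 0.6% in SE and half a point of power, if insulin is not prognostic. A gain needs a residual effect above about 0.3 HbA1c points at 25-31% prevalence (0.26-0.43 over 10-50%). At 0.5 points the gain is about 1% in SE and one point of power; at 0.75-0.8 points it is about 3-4% in SE. Both prevalence and effect are assumptions.

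The protection against imbalance is of similar size: 0.09 HbA1c points for a 2-SD imbalance with a 0.5-point effect. Averaged over randomisations that shift is zero.

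The case for acting is that the downside is small and bounded, the covariate is already defined, and in a linear model the added term leaves the target treatment difference unchanged.

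**What to change.** Before database lock and release of the randomisation code:

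1. Add insulin at baseline (Y/N, as in SAP 3.3) as a categorical fixed effect to the ANCOVA in SAP 3.5.
2. Make the matching edit in SAP 3.6.1 to the ANCOVAs for FPG and BMI SDS and to the logistic model for HbA1c below 7.0%. In the logistic model the odds ratio is conditional on the covariates, so its target changes slightly; the SAP should say so.
3. Record and justify the change in SAP section 4 as a departure from Protocol 17.3. Date it clearly, because subjects' allocations are revealed individually at Visit 17.
4. Keep the ANCOVA without the term as a sensitivity analysis, so that the other sensitivity analyses with the present covariates still have a like-for-like comparator.

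If the agreed primary model is to stay as it is, the minimum is to add the same multiple-imputation ANCOVA with the insulin term as a sensitivity analysis.

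The cost is one degree of freedom, a negligible rise in SE if insulin is not prognostic, a few lines of text, and a documented departure from the protocol model. No new data are needed.

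### The 80% power in Protocol 17.1 is not the power of the Rubin-pooled primary test; at SD 1.2 that test has about 62–71% power with 22% missing on liraglutide and 40% on placebo

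*SAP*

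**What the plan says.** SAP 3.5 and Protocol 17.3 use all available week 26 HbA1c values and impute the missing ones from regressions fitted to placebo completers. Liraglutide subjects are imputed from baseline covariates only. Placebo subjects may also use their week 10 and week 14 values. Each of 10,000 completed data sets is analysed by ANCOVA with treatment, strata and baseline HbA1c. Then: "The results obtained from analysing the datasets will be combined using Rubin's rule". Superiority is concluded if the 95% confidence interval "lies entirely below 0%; implying that the two sided p-value is less than 5" per cent. The same result opens the hierarchy for the confirmatory secondary endpoints (SAP 3.6.1).

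Protocol 17.1 assumes "a mean difference of 0.9% of liraglutide in combination with metformin" against placebo among subjects with week 26 data, and an SD of change "from baseline at week 26 assumed to be 1.2" per cent. The difference is diluted by the 22% withdrawal assumed for the active arm. The section states that no adjustment is made for placebo withdrawal, because those values will be imputed. On this basis "the sample size is set to 47 in each of the liraglutide and liraglutide placebo arms". The power claimed for that number, in the FAS, is 80%. SAP 3.4 only refers back to the protocol.

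**The concern.** The power calculation and the primary test use different standard errors. Section 17.1 treats all 94 week 26 values as observed. The test adds between-imputation variance to a within-imputation variance already computed on 94 values.

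The sampling variance of the estimate moves the other way. Imputed liraglutide values carry the placebo-completer mean, so the estimate shrinks towards (1 − liraglutide missing share) times the completer difference, and the two arms become positively dependent. Rubin's within-plus-between sum does not reflect that dependence. The interval that decides superiority is then wider than the repeated-sampling spread of the estimate, and the trial may miss the effect it was sized to detect. Neither document mentions this.

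**Working it through.** **Inputs.** From Protocol 17.1: n = 47 per arm, SD = 1.2, completer difference 0.9, liraglutide withdrawal pL = 0.22, no effect in withdrawn liraglutide subjects, and about 40% placebo withdrawal in the adult trial cited. From SAP 3.3 and 3.5: two-sided 5%, so 2.5% in the direction that counts.

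**The plan's figure.** Diluted difference 0.9 × 0.78 = 0.702. SE = 1.2 × √(2/47) = 0.248. A noncentral-t calculation gives 80.1% power at 47 per arm and reproduces all 15 sample sizes in Table 17-1. No between-imputation variance enters.

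**Closed form for the specified test** (no covariates, values missing completely at random, pP = 0.40):

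- Sampling variance = (1 − pL)² × SD² × [1/(n(1 − pL)) + 1/(n(1 − pP))] = 0.6084 × 1.44 × (1/36.66 + 1/28.2) = 0.0550, so SD 0.234.
- Within, under the null: W = 2 × 1.44/47 = 0.0613.
- Between: B = SD² × [(pL − pP)²/(n(1 − pP)) + (pL + pP)/n] = 1.44 × (0.0324/28.2 + 0.62/47) = 0.0207.
- Rubin variance 0.0819, SE 0.286. Ratio 0.286/0.234 = 1.22.
- One-sided level: Φ(−1.96 × 1.22) = 0.84%.
- Under the alternative the liraglutide arm is a mixture, which adds 0.22 × 0.78 × 0.81/47 = 0.0030 to W. Rubin SE = 0.291.
- Power: Φ((0.702 − 1.96 × 0.291)/0.234) = 71%.

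**Simulation of the SAP procedure** (imputation models from placebo completers, baseline-only for liraglutide, ANCOVA with strata and baseline, residual SD 1.2). At 22%/40% missing the mean Rubin SE is 0.30–0.32 and the SE ratio mostly 1.23–1.27, rising to about 1.31 if the imputation draws are fully proper. The one-sided level is mostly 0.8–0.9%, and power is 62–66%. With an SE equal to the true sampling SD, the same simulated designs would have 78–82% power (85% in the closed form), so the variance rule accounts for most of the shortfall. These runs assume values missing completely at random, 40% male, 70% in the older stratum, 30% on insulin and dropout spread evenly before week 26. The interim correlation was also assumed, at about 0.7 in the main runs.

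**Range of power for the Rubin test** (simulation and closed form together):

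| Missing, liraglutide / placebo | Residual SD | Power |
|---|---|---|
| 22% / 44% | 1.2 | 60–70% |
| 22% / 40% | 1.2 | 62–71% |
| 22% / 22% | 1.2 | 69–76% |
| 22% / 0% | 1.2 | 76–80% |
| 15% / 25% | 1.2 | 81–83% |
| 10% / 10% | 1.2 | 87–90% |
| 22% / 40% | 1.1 (assumed) | 72.5–79% |
| 22% / 40% | 1.0 (assumed) | 85–87% |

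The 44% row comes from Protocol 6.1, which expects 63 completers: 63 − 0.78 × 47 = 26.3 on placebo, or 56% of 47. That count is at Visit 26 (week 53), so it may overstate missing HbA1c at week 26.

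**The case against.** **Whether Rubin's variance is too wide is a debated choice of yardstick.** Without covariates, the factor (1 − pL) scales both the estimate and its sampling SD and cancels from the test. A test calibrated to the sampling SD is then a completers-only comparison: 0.9/0.3006 = 2.99, or 85% power, with no penalty for liraglutide dropout. The sampling SD even falls as liraglutide data are lost. With 22% missing on liraglutide and none on placebo it is 0.206, below the complete-data 0.248. A sponsor may reasonably prefer a variance that does not reward missing data. This stands, and it is why the Rubin test should not be replaced.

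**The departure is conservative.** This stands. A reader might infer that a miscalibrated interval puts the superiority claim or the hierarchy at risk. It does not, because the error rate lies below nominal.

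**No single power figure is fixed by the documents.** A reader might conclude that the trial has 66% power under the protocol's own withdrawal rates. The documents do not support that. The 40% is an adult-trial observation, and the only rate stated as assumed for this trial is 22% on active. Withdrawal is also not the same as missingness. Rescued subjects stay in and their data count, and withdrawn subjects are asked for Visit 17 procedures, whose results count if they fall within the visit window. Using 1.2 as residual SD also gives no credit for baseline adjustment. A range is the right form.

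**Regulatory origin and timing.** The revised primary analysis was requested by the FDA, and SAP 2.0 is dated 25 June 2018 against a planned last visit (Visit 26) of 15 July 2018. Restating power cannot change enrolment. It can still correct a stated figure and help in reading a borderline result.

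**Conclusion.** The point holds as a mismatch between the stated power and the specified test. The 80% in 17.1 belongs to a complete-data comparison. At SD 1.2 and 22% missing on liraglutide, the Rubin-pooled test falls short of 80% once placebo missingness reaches that same 22%, and by roughly 9 to 18 percentage points at 40%. The shortfall disappears at lower missingness or at a residual SD of about 1.0, and it is small or moderate at 1.1. Those residual SDs are assumptions.

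The documents do not support calling Rubin's rule an error here. Its conservatism is defensible, but the plan neither states it nor allows for it in the sample size.

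**What to change.** In Protocol 17.1, restate the power for the Rubin-pooled test as specified, as a range over week 26 missingness in each arm and over residual SD, with the assumptions listed. Add a sentence saying that the Rubin variance is conservative for this placebo-based estimate. Keep the Rubin test as the sole decision rule.

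Optionally, pre-specify in SAP 3.5 a descriptive bootstrap interval for the same estimate, stratified by arm, with the imputation models refitted in each resample. Label it as having no role in the decision, so that it cannot compete with the Rubin interval if the two disagree about zero. Note beside it that the sampling variance shrinks as liraglutide data are lost.

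The cost is a short paragraph and some computing. The stated power becomes less favourable, and the optional interval would need explaining.
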